RSV Season 1 MK-1654 Group Part 2 Scheduled Day and Window (Days):	60 (28-32 days after Dose 2)	150 (±5)	180 (±2 ^a)	240 (±5)	365 (+14) ^b	If indicated	If indicated	See SoA in Section 1.3.1.1 for activities before the Day 60 visit. Participant's treatment assignment will be unblinded at the Day 60 visit (28-32 days after Dose 2). ^a Continue weekly contact, each with a ±2-day window. ^b Participants continuing into RSV Season 2 will begin RSV Season 2 up to 4 weeks before the start of their second RSV season (246 to 393 days after RSV Season 1 Dose 1) (Section 4.2.1.1.1). See SoA in Section 1.3.2 for RSV Season 2. Participants not eligible for RSV Season 2 will be followed through the RSV Season 1 Day 365 TC.
Administrative Procedures								
Concomitant Medication Review	X	X	X	X	X	X ^c	X	Only concomitant medications associated with an AE/SAE will be recorded. ^c Concomitant medications will be collected for 42 days following an additional post-surgery dose of MK-1654.
MK-1654 Administration						X		See Section 6.1, Section 6.2, and Section 8.1.8.1.
Provide or Reactivate Device for eDiary Data Collection and Provide LAR Training						X		For participants using a study-provided device, provide eDiary if LAR previously returned the original study-provided device.
Review eDiary with LAR						X		Safety follow-up for 42 days after post-surgery dose. See Section 8.3.5.
Collect eDiary Device from LAR				X				
Review Inclusion/Exclusion Criteria				X				For participants enrolled in 2 RSV seasons, review inclusion/exclusion criteria for RSV Season 2 to ensure participant meets RSV Season 2 eligibility requirements. See Section 5.1.1 and Section 5.2.1.

Study Period	Follow-up RSV Season 1 (Day 60 Visit through end of RSV Season 1)							Notes
Visit Number/Title	4A	5	Weekly contact ends	6	TC	Post-surgery Follow-up	UNSCH	See Section 8.13 for description of study visits. Post-surgery follow-up visit for participants who undergo 1) ECMO or 2) surgical intervention and require cardiopulmonary bypass during the procedure for CHD during the RSV season and are recommended during Sponsor consultation to receive additional study intervention (Section 8.1.8.1). UNSCH for respiratory infection and AESI assessment and early withdrawal, if indicated.

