Visit Number/Title	4A	TC	4B	TC	4C	TC	5	Weekly contact ends	6	TC	Post- surgery Follow- up	UNSCH	See Section 8.13 for descriptions of study visits. Post-surgery follow-up visit for participants who undergo 1) ECMO or 2) surgical intervention and require cardiopulmonary bypass during the procedure for CHD during the RSV season and are recommended during Sponsor consultation to receive additional study intervention (Section 8.1.8.1). UNSCH for respiratory infection and AESI assessment and early withdrawal, if indicated.
RSV Season 1 Palivizumab Group Part 2 Scheduled Day and Window (Days):	60 ^a	74 ^a	90 ^{a,b}	104 ^{a,b}	120 ^{a,b}	134 ^{a,b}	150 (±5)	180 (±2 ^c)	240 (±5)	365 (+14) ^d	If indicated	If indicated	See SoA in Section 1.3.1.1 for activities before the Day 60 visit. Participant's treatment assignment will be unblinded at the Day 60 visit (28-32 days after Dose 2). ^a Doses 3-5 must be administered between 28-32 days after the previous dose. Safety follow-up TCs must be conducted 14 days (±2 days) after each dose. ^b For those who do not require a dose at the Day 90 or 120 visits, the respective visit(s) and the associated 14-day safety follow-up TC will not be conducted. ^c Continue weekly contact, each with a ±2-day window. ^d Participants continuing into RSV Season 2 will begin RSV Season 2 up to 4 weeks before the start of their second RSV season (246 to 393 days after RSV Season 1 Dose 1) (Section 4.2.1.1.1). See SoA in Section 1.3.2 for RSV Season 2. Participants not eligible for RSV Season 2 will be followed through the RSV Season 1 Day 365 TC.
Administrative Procedures													
Concomitant Medication Review	X	X	X	X	X	X	X	X	X	X	X	X	Only concomitant medications associated with an AE/SAE will be recorded.
Palivizumab Administration	X		X ^e		X ^e						X		See Section 6.1, Section 6.2, and Section 8.1.8.1. ^e Doses 4 and 5 will be administered as applicable (see Section 6.1 and Section 2.2.4).

Study Period	Follow-up RSV Season 1 (Day 60 Visit through end of RSV Season 1)												Notes
	4A	TC	4B	TC	4C	TC	5	Weekly contact ends	6	TC	Post- surgery Follow- up	UNSCH	

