All study participants will receive 2 blinded doses before unblinding in RSV Season 1:

- MK-1654 group: MK-1654 (Dose 1) and placebo (Dose 2)
- Palivizumab group: palivizumab (Dose 1 and Dose 2)

All participants, irrespective of treatment group, will have safety monitoring (AEs and SAEs), efficacy surveillance to monitor the incidence of RSV-associated MALRI and hospitalization, and blood sample collection as described in the SoA (see Section 1.3.1.1 SoA – RSV Season 1 Part 1).

Participant's treatment assignment will be unblinded at the Day 60 visit before any visit procedures. Participants in the MK-1654 group do not have any additional planned doses in RSV Season 1 and will continue with safety monitoring, efficacy surveillance, and blood sample collection as described in the SoA (see Section 1.3.1.2 SoA – RSV Season 1 Part 2 – MK-1654 Group). Participants in the palivizumab group will receive at least 3 and up to 5 single doses of palivizumab, once every 28 (+4) days (inclusive of dosing day; minimum of 28 days between doses), depending on the timing of enrollment relative to the RSV season. For calculating the visit windows for subsequent administrations, the day of the previous administration is considered Day 1. These participants will continue with safety monitoring and efficacy surveillance as described in the SoA (see Section 1.3.1.3 SoA – RSV Season 1 Part 2 – Palivizumab Group).

For infants enrolled and consented to participate in RSV Seasons 1 and 2, inclusion/exclusion criteria will be rechecked at the Day 240 visit for eligibility to continue in RSV Season 2 (see Section 5.1 and Section 5.2). Participants still eligible will begin the RSV Season 2 between 246 to 393 days after RSV Season 1 Dose 1, depending on the timing of enrollment relative to the RSV season (see Section 8.1.8.1). Participants in the palivizumab group who are continuing in RSV Season 2 will have blood sample collection at the Day 240 visit to serve as the baseline for RSV Season 2. All participants not continuing in RSV Season 2 will be monitored for safety for 365 days after receiving the first dose in RSV Season 1.

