4.2.1 Rationale for Endpoints

4.2.1.1 Efficacy Endpoints

Secondary and tertiary efficacy endpoints for this study are to estimate RSV-associated outpatient and inpatient MALRI (diagnosed as in [Table 1](#)) in RSV Seasons 1 and 2. The diagnostic criteria are based on published literature and information from clinical studies,

RSV expert panels, and WHO and CDC guidelines [Manoha, C., et al 2007] [Nair, H., et al 2010] [Simoes, E. A. F., et al 2015]. Cough or difficulty breathing are included based on the case definition for severe and very severe LRI by the expert panel on RSV vaccine development convened by the WHO [Simoes, E. A. F., et al 2015].

RSV-associated MALRI represents most of the RSV disease burden and is a clinically important and well-defined RSV disease endpoint across geographies and healthcare settings [Nair, H., et al 2010] that has been recommended by RSV prophylaxis trial expert committees [Simoes, E. A. F., et al 2015]. A secondary efficacy endpoint is the estimation of efficacy against RSV-associated MALRI from Day 1 through Day 150 postdose (the length of a typical RSV season in a temperate climate) in RSV Season 1. Assessment of efficacy against RSV-associated hospitalization from Day 1 through Day 150 postdose in RSV Season 1 is also planned as a secondary efficacy endpoint as this is an outcome of clinical importance to healthcare practitioners and healthcare systems.

Table 1 Respiratory Syncytial Virus (RSV)-associated Medically Attended Lower Respiratory Infection (MALRI) Diagnostic Criteria

Signs/Symptoms	Indicators of LRI/Severity	RSV
Endpoint definition requires at least 1 from each column seen in an outpatient or inpatient clinical setting (outpatient clinic, clinical study visit, Emergency Department, urgent care center, or hospital) and confirmed or observed by the investigator.		

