8.2.2 Respiratory Infection Assessment

8.2.2.1 Requirements for Scheduling a Respiratory Infection Assessment

To identify potential cases of RSV-associated LRI, participants with any respiratory infection symptoms should be assessed at the site by the investigator or medically qualified designee. RSV-associated MALRI is defined in Section 4.2.1.1.

A respiratory infection assessment is required when:

- Respiratory infection symptoms are reported (see Section 8.2.1).
- New or worsening LRI signs/symptoms arise during an existing respiratory infection episode.
- The participant is seen in an outpatient or inpatient clinical setting for respiratory infection symptoms.

The respiratory infection assessment should be performed within 3 days of symptom onset or worsening.* If this is not possible or the visit for the assessment is missed, it can be performed within 12 days of symptom onset or worsening.*

***Note:** Symptom onset or worsening may refer to the symptom onset or worsening that led to the outpatient visit or hospital admission.

A respiratory infection assessment may occur during an unscheduled visit or at a scheduled study visit if that visit occurs within the time requirements noted above.

Every attempt should be made to assess the participant at the study site. If this is not possible, a home visit or visit to an alternate study site may be used, where available and when

permitted by local regulations and IRB/IEC. In the case of a home visit or visit to an alternate study site, all indicated study procedures should be performed, including NP sample collection for RT-PCR testing at the central laboratory.

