8.3.1 Physical Examinations Including Length and Weight

A complete physical examination and brief directed physical examinations will be conducted by an investigator or medically qualified designee and consistent with local requirements. Length and weight will also be measured and recorded.

The complete physical examination should include an assessment of the head, eyes, ears, nose and throat, skin, lymph nodes, neurological system, and musculoskeletal system as well as auscultation of the heart and lungs, and an examination of the abdomen.

The brief directed physical examination should include a general assessment for respiratory distress, auscultation of the heart and lungs, and examination of the abdomen.

Investigators should pay special attention to clinical signs related to previous serious illnesses.

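### After the Day 60 unblinding, MALRI can be ascertained unequally: only the palivizumab arm has extra study contacts before Day 150, and no planned analysis isolates their effect

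*Combined protocol and SAP*

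**What the plan says.** **Case definition.** Table 1 (Section 4.2.1.1) accepts signs "seen in an outpatient or inpatient clinical setting (outpatient clinic, clinical study visit, Emergency Department, urgent care center, or hospital", if the investigator confirms or observes them. Section 8.2.2.1 adds: "A respiratory infection assessment may occur during an unscheduled visit or at a scheduled study visit".

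**Unblinding.** Section 4.1 states that "treatment assignment will be unblinded at the Day 60 visit before any visit procedures". It also says: "Participants in the MK-1654 group do not have any additional planned doses in RSV Season 1".

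**Schedules after Day 60.** In Section 1.3.1.2 (MK-1654) the next in-person visit after Day 60 is Day 150. Section 1.3.1.3 (palivizumab) adds visits at Days 90 and 120 and calls at Days 74, 104 and 134. The Day 90 and 120 visits are conditional: a footnote that begins "For those who do not require a dose at the Day 90 or 120 visits, the respective visit(s" drops the visit and its follow-up call when no dose is due. The visits include a directed examination and vital signs. Section 8.3.1 says: "The brief directed physical examination should include a general assessment for respiratory distress, auscultation of the heart and lungs". Section 8.3.2 adds respiratory rate and SpO2. Section 8.3.5 has palivizumab caregivers record AEs in the eDiary for 14 days after each dose.

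**Common surveillance.** Both schedules carry the same note, "Continue weekly contact, each with a ±2-day window", through Day 180. Under Sections 8.2.1 and 8.2.2, any reported respiratory symptom leads to a site assessment in either arm.

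**Analysis.** Sections 9.5.1 and 9.6.1 contain no analysis by route of case identification and none restricted to the blinded period. The synopsis lists no Clinical Adjudication Committee.

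**The concern.** The between-arm efficacy estimate assumes that a case is equally likely to be found in either arm. From Day 60 to Day 150, which is (150 − 60)/150 = 60% of the secondary endpoint's window, allocation is known and the planned contacts differ by arm. Each extra contact is an opportunity to find a palivizumab case that would go unfound in an MK-1654 infant.

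The common surveillance does not close every gap:

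- Rales/crackles and hypoxemia qualify as LRI signs in Table 1 but are not on the caregiver list in Section 8.2.1. They are found on examination. An infant with a known cough and no LRI sign at first assessment gets a further planned examination at Day 90 or 120 only in the palivizumab arm.
- Every palivizumab infant is planned at least three doses, so the follow-up after Dose 3 applies to the whole arm. Respiratory symptoms or fever entered in the eDiary prompt a call from the site (Sections 8.3.3 and 8.3.5).

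The Day 150, Day 180, end-of-season and RSV A/B efficacy estimates all use this case definition. RSV-associated hospitalization requires admission, so a study visit alone cannot create a case there.

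**Working it through.** **1. Planned contacts, Days 61 to 149**

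| Contact | MK-1654 | Palivizumab |
|---|---|---|
| Weekly contact | Yes | Yes |
| Symptom-triggered site assessment | Yes | Yes |
| Scheduled in-person visit | None | Day 90 if Dose 4 is due, Day 120 if Dose 5 is due |
| Post-dose call | None | Day 74; Days 104 and 134 if the dose was due |
| Post-dose eDiary | None planned | 14 days after each dose |

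**2. The plan's own precision (Table 8)**

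The exact Poisson limits are χ²(0.025; 2x)/2n and χ²(0.975; 2x + 2)/2n. With n = 450 (500 less 10% attrition) and x = 450 × 0.045 = 20.25, they are 0.0276 and 0.0693, which matches the stated 0.028 and 0.069. With n = 500 the upper limit is 0.0678, which does not match. For efficacy at 0.045 vs 0.06, 20,000 simulated trials with 450 per arm give an average interval of −37.7 to 55.9. The plan states −35.9 to 56.5. The difference is consistent with the noise of the plan's 1000 simulations, so Table 8 is a sound reference for scale.

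**3. Size of the visit mechanism**

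Let s be the share of true cases found by the routes common to both arms. Let f be the share of the risk period in which a Day 90 or 120 visit could pick up an otherwise missed case. The MK-1654 arm finds s, and the palivizumab arm finds s + f(1 − s). The observed relative risk is therefore the true one multiplied by

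m = s / (s + f(1 − s)).

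The documents do not give s, so it is varied as an assumption. For f, take both visits, the 12-day sampling window of Section 9.5.1 and uniform risk over 150 days: f = 2 × 12/150 = 0.16. Example at s = 0.70: m = 0.70/(0.70 + 0.16 × 0.30) = 0.70/0.748 = 0.9358, and observed efficacy is 1 − 0.75 × 0.9358 = 29.8%.

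| s | m | True 0% seen as | True 25% seen as | True 40% seen as |
|---|---|---|---|---|
| 0.95 | 0.9916 | 0.8% | 25.6% | 40.5% |
| 0.90 | 0.9825 | 1.7% | 26.3% | 41.0% |
| 0.80 | 0.9615 | 3.8% | 27.9% | 42.3% |
| 0.70 | 0.9358 | 6.4% | 29.8% | 43.9% |
| 0.50 | 0.8621 | 13.8% | 35.3% | 48.3% |

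If s = 1 there is no bias. With only one extra visit (f = 12/150 = 0.08) and s = 0.90, 25% is seen as 25.7%.

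In cases: with 450 × 0.06 = 27 palivizumab cases found by common routes, the visits add 27 × 0.16 × (1 − s)/s. That is 0.48 case at s = 0.90 and 1.85 cases at s = 0.70.

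**4. Non-uniform risk**

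If 30% of risk fell in the visit windows (Days 78 to 90 and 108 to 120) and s = 0.70, then m = 0.70/(0.70 + 0.30 × 0.30) = 0.8861, and 25% is seen as 33.5%. Some clustering is plausible. Enrollment opens 4 weeks before season onset (Section 4.1). In the US season described in Section 4.2.1.1.1, with onset in early November and peak in late December, the earliest enrollees reach the peak near Days 80 to 90.

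**5. Limits of the model**

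It leaves out the calls and eDiary follow-up, which would raise f. It also treats every day of the sampling window as usable, although LRI signs must be seen in a clinical setting, which lowers f.

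**The case against.** The strongest reply is that common surveillance already finds most cases. Both arms have weekly contact to Day 180, and caregivers are told to call the site. Even cough or congestion leads to an assessment, normally within 3 days, with a nasopharyngeal sample if signs are present. That triggered assessment is itself a study visit, so MK-1654 infants can meet the same setting criterion. A case also needs cough or difficulty breathing, which a caregiver can notice, and a central-laboratory PCR result in the FAS. All of this stands, and it confines the problem to cases missed by every common route.

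A reader might infer more than the documents support:

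- **That palivizumab cases are certainly found more often and efficacy is certainly inflated.** Under the model above, 3 visit-only cases on top of 27 would need 0.16(1 − s)/s = 3/27, so s = 0.59. Common surveillance would have to miss about 41% of cases, and nothing in the documents suggests that.
- **That all the error runs one way.** This is true of the extra contacts. Knowledge of allocation by caregivers and investigators is a separate risk, and the documents do not establish its direction.
- **That the whole open-label 60% is unequally examined.** The in-person difference is at most two visits per infant.
- **That Day 150 MALRI is the only between-arm efficacy estimate.** Sections 3 and 9.6.1 also plan Day 180, end-of-season and RSV A/B estimates.

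Monthly comparator dosing makes some asymmetry unavoidable, and the endpoint is secondary with no hypothesis test. That lowers the severity but does not explain why no sensitivity analysis is planned.

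**Conclusion.** The risk of differential ascertainment after Day 60 is real and partly mitigated, and the plan neither quantifies nor examines it. The extra palivizumab contacts can only add palivizumab cases, so that mechanism favours MK-1654. If common routes find 70% to 95% of cases, risk is uniform and both extra visits take place, a true 25% is seen as about 26% to 30%. It would be higher with lower s or clustered risk, and lower when only one extra visit or none is held.

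This is small beside the Table 8 interval at 25%, which is 56.5 + 35.9 = 92.4 points wide. But that interval reflects sampling error only and does not cover a one-directional shift. The point is worth acting on because the remedy is cheap and would be less credible if added after the data are seen. It is not a must-fix.

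**What to change.** **Section 9.6.1**

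1. Prespecify the same modified Poisson efficacy estimate in the FAS for the blinded period, from Day 1 to each infant's Day 60 unblinding. The schedule is common to both arms over that time.
2. Record how each respiratory episode was first identified. Add a FAS sensitivity analysis that excludes, in either arm, MALRI first identified only through a scheduled visit or an arm-specific post-dose call or eDiary review. Keep cases whose symptoms were reported through a common route and then assessed at a coinciding scheduled visit. A visit-type flag alone will not do: Section 8.2.2.1 lets a scheduled visit replace a triggered one, so dropping by visit type would remove palivizumab cases that would have counted in the MK-1654 arm. Report the result beside the main estimate, because it may over-correct: some excluded cases would have been found anyway.

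**Section 4.1**

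3. At the Day 60 visit, record respiratory surveillance, examination and AE review before allocation is opened, and align this with the pre-unblinding data lock in Section 9.2.

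**Cost.** One extra data field, SAP wording, and a sentence on the order of Day 60 procedures. The sensitivity estimates will have fewer cases and wider intervals. Under uniform risk the blinded period holds 60/150 = 40% of cases, or about 0.4 × 20.25 = 8 vs 0.4 × 27 = 11 at the plan's 4.5% and 6.0%. A difference between the blinded-period and Day 150 estimates could also reflect a change in protection over time, so it should not be read as bias alone.

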4.2.1.1.1 RSV Season Definition

RSV epidemics begin each year near the equator and then move toward temperate regions. Global patterns in monthly RSV activity have been observed and annual average percentage of RSV activity calculated for 152 sites globally in an ongoing review of RSV seasonality studies and online datasets by RESCEU [You, Li 2017].

In the US, RSV season onset has ranged from late October to late January and season offset has ranged from late January to early April in all 10 DHHS regions, except in Florida, which has an earlier RSV season onset and longer duration, as reported by the CDC NREVSS [Haynes, A. K., et al 2014]. During the 2013–2014 RSV season, similarly to previous national patterns, RSV began circulating nationally in early November and ended in late March, with circulation peaking at 24% (the number of RSV-positive specimens among all respiratory specimens tested) in late December. The RSV season (onset, offset, peak, and duration) is defined nationally, by DHHS region, and by state, based on CDC analysis of

RSV laboratory detections reported to the NREVSS. The CDC and WHO define the onset of the RSV season as a 10% threshold of RSV-positive specimens during 2 consecutive weeks.

In the European Union, the RSV season is typically November to April with a peak in the midwinter months [European Medicines Agency 2017]. The European influenza surveillance system captures RSV detection through the ILI or ARI surveillance system from 21 European Union countries, as reported for the 2014-2015 RSV season by the ECDC [European Center For Disease Prevention And Control 2015].

In the Southern Hemisphere, the RSV season is typically April to August, peaking in July in temperate regions. Tropical and subtropical regions have different RSV season profiles, as detailed in the regional RSV seasonality guidance document (or equivalent).

Infants entering their first RSV season are typically under 9 months of age. For example:

- An infant born in the Northern Hemisphere in January during their first RSV season may be enrolled during this RSV season. When the infant is 9 months old, they will be entering their second RSV season.
- An infant born in a temperate region of the Southern Hemisphere in June during their first RSV season may be enrolled during this RSV season. When the infant is 9 months old, they will be entering their second RSV season.

These considerations support enrollment of at least 90% of participants who are 0 through 8 months of age (ie, up to 8 months and 29 days), with up to 10% of the remaining participants ≥ 9 months of age to allow for potential moves between hemispheres in infancy (ie, where an infant may be 9 to 12 months of age and still in their first RSV season).

The Sponsor will define the expected start and end of the RSV season for each region participating in the study, based on several prior years' RSV seasons, as determined by national surveillance and/or available peer-reviewed literature. Detailed instructions will be provided in the regional RSV seasonality guidance document (or equivalent).

